## **11.3 Calculation or derivation of pharmacodynamic variable(s)**

### **ADP-induced inhibition of platelet aggregation**

The inhibition of platelet aggregation, (IPA), from pre-dose baseline will be calculated at each time post-dose using the following formula for ADP-induced aggregation (final extent):

$$IPA(\%) = 100 \times \frac{(PA_{BL} - PA_T)}{PA_{BL}}$$

Where  $PA_T$  is the response at any post treatment time 'T', and  $PA_{BL}$  is the response at pre-dose baseline on Day 1. Percentage inhibition will be restricted to the closed interval [0,100]; any data falling outside this range will be truncated to the appropriate limit.

The area under the time-effect curve (AUEC) for IPA will be calculated over the dosing interval from the respective IPA vs. time curves using the linear trapezoidal rule.

Time to peak IPA ( $TIP_{A_{max}}$ ) will be the time of the maximum final extent IPA within a dosing interval.

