### **Outcome variable(s):**

#### **Primary outcome variables:**

- **Pharmacodynamic**
  - IPA (final extent) induced by 20 $\mu$ M adenosine diphosphate (ADP) at each assessment point after single and multiple doses of ticagrelor measured by Light-Transmittance Aggregometer (LTA)

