### **3.1 Overall study design and flow chart**

This is an open label, single centre, randomised, Phase IV, pharmacokinetic, pharmacodynamic, and safety study to evaluate single and multiple doses of 45, 60, and 90 mg of ticagrelor in Chinese patients with stable coronary heart disease.

The timing of study assessments is outlined in the Study Plan (Table 1). Patients will undergo screening assessments during the maximum 19-day period preceding administration of the first dose of study drug on Day 1. Patients will report to the CPU on Day -2 and will remain confined there until Day 8 for the fully completion of study procedures of Day 7. In addition, patients will return to the CPU for a follow up visit 2-5 days after the last dose. Each patient will participate in the study for approximately 33 days.

Approximately 36 patients with stable coronary heart disease will enter this study, with 12 patients randomly enter into each of three treatment groups (Treatment A, Treatment B and Treatment C). Patients will receive ticagrelor as a single dose on Day 1, followed by a bid dose for 4 days (Day 3 to Day 6), and a single dose on Day 7. On Day 2, no treatment will be given, but blood samples will be obtained.

Treatment A: A single dose of ticagrelor 45 mg on Day 1 followed by 45 mg twice daily (bid) on Days 3-6 and a 45mg single dose on Day 7.

[figure not shown]
Treatment B: A single dose of ticagrelor 60 mg on Day 1 followed by 60 mg twice daily (bid) on Days 3-6 and a 60mg single dose on Day 7.

Treatment C: A single dose of ticagrelor 90 mg on Day 1 followed by 90 mg twice daily (bid) on Days 3-6 and a 90mg single dose on Day 7.

Safety assessments including physical examinations, laboratory assessments, AE and vital sign measurements will be performed according to the schedule in the Study Plan (Table 1). PK and PD blood samples will be obtained at the times noted in the Blood Sampling schedule (Table 2).

All treatment will be administered in an open-label design. To be included in the study the patients must stay on ASA, 75-100mg, which will be maintained at a constant dose throughout the study period.

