**Table 2            Blood Sampling**

Assessment	Day 1	Day2	Day3	Day 7
Samples for PK	0, 0.5, 1, 2, 3, 6, and 12 h	24 and 36 h	48 h	0, 0.5, 1, 2, 3, 6, 12 h
Samples for IPA and P2Y 12 measured by VerifyNow	0, 0.5, 1, 2, 3, 6, and 12 h	24 and 36 h	48 h	0, 0.5, 1, 2, 3, 6, 12 h

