## PRU

$P2Y_{12}$  reaction units (PRU) will be measured by VerifyNow™  $P2Y_{12}$  assay. The PRU data will be presented as the absolute PRU at each timepoint and percent reduction of the  $P2Y_{12}$  receptor from baseline. Percent reduction will be calculated as percent change from baseline (pre-treatment) PRU versus each timepoint post treatment using the following formula

$$\% \text{ Reduction from baseline} = 100 \times \frac{(PRU_{BL} - PRU_T)}{PRU_{BL}}$$

Where  $PRU_T$  is the response at any post treatment time 'T', and  $PRU_{BL}$  is the response at pre-dose baseline on Day 1.

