### **12.2.3 Pharmacodynamic data**

IPA(final extent), absolute PRU and percent reduction of PRU from baseline will be listed by patient and time, and summarized by treatment group at each time point using n, arithmetic mean, SD, median, minimum and maximum TIPAmax and AUEC for final extent IPA will be summarized descriptively by treatment group and study Day 1 and 7.

Profiles of IPA (final extent), percent inhibition and percent reduction of PRU will be plotted per patient for Day 1 (0-48h post dose) and Day 7 (0-12h post dose). The corresponding arithmetic mean ( $\pm$  SD) by time point and treatment group will be plotted in one graph with treatment group indicated.

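### Truncating IPA to 0–100 before averaging raises the mean and shrinks the SD at time points where true inhibition is near zero; an untruncated summary and a count of truncated values should be added

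*Protocol*

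**What the plan says.** The primary outcome is "IPA (final extent) induced by 20" µM ADP, at each assessment point after single and multiple doses. Section 11.3 defines it as IPA(%) = 100 × (PA_BL − PA_T)/PA_BL, where PA_BL is one pre-dose value on Day 1, and adds: "Percentage inhibition will be restricted to the closed interval [0,100]; any data falling outside this range will be truncated to the appropriate limit".

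Section 12.2.3 says that IPA is "summarized by treatment group at each time point using n, arithmetic mean, SD, median, minimum and maximum". Individual profiles are plotted, and the mean ± SD "by time point and treatment group will be plotted in one graph with treatment group indicated".

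Table 2 schedules Day 1 samples at "0, 0.5, 1, 2, 3, 6, and 12 h", then 24, 36 and 48 h. Section 3.1 adds: "On Day 2, no treatment will be given, but blood samples will be obtained". Day 7 sampling ends at 12 h.

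The PRU percent reduction in section 11.3 has the same form of formula and the same Day 1 baseline, but no truncation is stated for it. The protocol states neither an untruncated IPA summary nor a count of truncated values.

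**The concern.** The two limits look symmetric but are not. To exceed 100, IPA needs negative aggregation. To fall below 0, it needs only a post-dose reading above the single baseline reading. When the drug has no effect, ordinary measurement variation does this about half the time. Setting those values to 0 discards the downward errors and keeps the upward ones.

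The study is descriptive, so the reported means, SDs and plotted profiles are themselves the result. No later inferential step would correct them. The schedule deliberately includes early and late points after a single dose. If inhibition there is close to zero, a truncated mean shows some inhibition where there may be none, the SD looks tighter than it is, and the doses may look closer together than they are.

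**Working it through.** **Inputs from the protocol.** The formula, the single Day 1 baseline, the limits [0,100], the mean and SD summaries, the sampling times, and 12 patients per group. The protocol gives no SD and no expected value for IPA, so there is no stated figure to reproduce. The SD of 10 to 20 points and the true means below are assumptions.

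**Direction, with no assumed SD.** For low IPA only the lower limit acts, so the reported value is max(0, x). Since max(0, x) ≥ x, the mean can only rise. Truncation never widens the gap between two values, so the SD can only fall.

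**Size.** For X normal with mean μ and SD s, E[max(0, X)] = μ·Φ(μ/s) + s·φ(μ/s). Example with μ = 10, s = 15: 10 × 0.7475 + 15 × 0.3194 = 12.27. Mean after truncation (SD after truncation in brackets):

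| True mean | s = 10 | s = 15 | s = 20 |
|---|---|---|---|
| 0 | 3.99 (5.8) | 5.98 (8.8) | 7.98 (11.7) |
| 10 | 10.83 (8.7) | 12.27 (11.8) | 13.96 (14.9) |
| 20 | 20.08 | 20.64 | 21.67 |
| 30 | 30.00 | 30.13 | 30.59 |

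At μ = 0 the variance after truncation is s²(1/2 − 1/(2π)) = 0.341 s², so the SD is 0.584 s, about 58% of its value.

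Against sampling error with 12 patients and s = 15, the standard error is 15/√12 = 4.33. The shift is 5.98/4.33 = 1.4 standard errors at true IPA 0, and 2.27/4.33 = 0.5 at true IPA 10.

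**Dose differences, equal SDs.** From the table, for s = 10, 15, 20:
- True 0 against 10: 10.83 − 3.99 = 6.8; 12.27 − 5.98 = 6.3; 13.96 − 7.98 = 6.0, instead of 10.
- True 10 against 20: 9.3, 8.4 and 7.7, instead of 10.

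**Dose differences, unequal SDs.** Mean 5 with SD 10 becomes 6.98, and mean 15 with SD 25 becomes 19.22. The difference grows from 10 to 12.2. Compression therefore depends on similar SDs.

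**Which time points.** Section 13 gives a half-life of about 12 h and expects low drug levels by 48 to 72 h. Section 1.1 gives about 7 h. With 12 h, the share remaining at 24, 36 and 48 h is 25%, 12.5% and 6%. With 7 h, about 1% remains at 48 h. So 48 h is the best-supported point. The protocol does not show that IPA is near zero at 0.5, 24 or 36 h; it is only possible.

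**AUEC.** It is taken over the dosing interval, here 12 h, so 24 to 48 h values do not enter. The 0.5 h value has trapezoid weight (0.5 + 0.5)/2 = 0.5 h. A shift of 6 points there adds 3 %·h, against 50 × 12 = 600 %·h for an assumed average IPA of 50%, which is 0.5%.

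**Check on the aggregation scale.** Assumed: true aggregation 60 (SD 12) and measurement noise of SD 5 to 10 at baseline and post-dose. With no drug effect, the raw mean is −0.8 to −3.7 and the truncated mean +4.6 to +8.6; the median stays at 0. The lowest 1% of raw values lie below about −37 to −97. With a constant true IPA of 20, the raw mean is 19.3 down to 17.0 and the truncated mean 19.8 to 21.2. Raw IPA is thus left-skewed and its mean is biased low, because it divides by one noisy baseline.

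**The case against.** The rule is explicit and prespecified, and one can hold that inhibition is by definition a bounded quantity. Section 12.2.3 also gives the median, minimum and maximum, patient listings and individual profiles, and PRU is measured at the same times without truncation. No test or power figure depends on IPA. The assumed SD and the zero true mean are not in the protocol, and zero is the worst case. Removing the truncation is no clean cure either, since the raw mean is biased low and one extreme value can dominate a group of 12.

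Most of this stands and limits the point. It does not remove it: disclosure leaves the distortion of the mean and SD in place, those are the plotted statistics, and the reader is not told how many values were reset. The planned listings and minimum do not help if they carry truncated values, and the protocol plans no untruncated ones.

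A reader might infer more than the documents support:
- That truncation always compresses dose differences. It need not when SDs differ.
- That AUEC is materially distorted. The weights above show it barely moves.
- That the different handling of PRU is a contradiction. These are different assays on different scales, and nothing says they must agree numerically.
- That the truncation should simply be deleted. At true IPA around 20 the truncated mean is usually nearer the truth than the raw mean.

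**Conclusion.** The point holds for the mean and SD at time points with true IPA near zero: most plausibly 48 h after the Day 1 dose, possibly 0.5 h and 24 to 36 h. The direction follows from the protocol's own formula and rule. The size rests on an assumed, roughly normal IPA with SD 10 to 20 points. On that basis the mean is raised by 4 to 8 points at true IPA 0 and by about 1 to 4 at true IPA 10, and at zero the SD falls to about 58%. With similar SDs across doses, a 0 against 10 contrast appears as 6 to 7 points.

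Above about 30% IPA the effect is negligible, so the peak is untouched, and probably Day 7 as well. Group medians whose middle values lie above 0 do not change. It would be wrong to read this as a bias across the whole IPA profile or as a flaw in any test: the study has none. An analysis plan not shown here may add summaries, but the protocol itself fixes the truncation and the statistics that it feeds.

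**What to change.** In sections 11.3 and 12.2.3:
- Keep the truncated summary if wanted, labelled as such.
- Also summarise and plot untruncated IPA (mean, SD and median) by dose and time point.
- Report the number of values truncated at each limit, by dose and time point.
- Base statements on onset, residual inhibition and dose separation at low-IPA points on the untruncated summary. Use the median as the main measure, because raw IPA is left-skewed.

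The cost is one extra table and figure, with no new sampling. Some individual values will be clearly negative and need a footnote explaining the single noisy baseline.

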## PRU

$P2Y_{12}$  reaction units (PRU) will be measured by VerifyNow™  $P2Y_{12}$  assay. The PRU data will be presented as the absolute PRU at each timepoint and percent reduction of the  $P2Y_{12}$  receptor from baseline. Percent reduction will be calculated as percent change from baseline (pre-treatment) PRU versus each timepoint post treatment using the following formula

$$\% \text{ Reduction from baseline} = 100 \times \frac{(PRU_{BL} - PRU_T)}{PRU_{BL}}$$

Where  $PRU_T$  is the response at any post treatment time 'T', and  $PRU_{BL}$  is the response at pre-dose baseline on Day 1.

### 11.3.1 Calculation or derivation of the relationship between pharmacokinetic and pharmacodynamic variables

Relationship between ticagrelor plasma concentration and effect on PD variables will be presented graphically. If appropriate, concentration-effect relationships will be explored.

## 12. STATISTICAL METHODS AND SAMPLE SIZE DETERMINATION BY ASTRAZENECA

The statistical analysis will be performed by Biostatistics Group using SAS® Version 9.1, or higher.

### 12.1 Description of analysis sets

Throughout the analyses, erroneously treated patients (eg, those randomised to treatment A but actually given treatment B) will be accounted for in the actual treatment group. Patient inclusion in each of the analysis sets will be determined from database lock.

### **12.1.1 Safety analysis set**

All patients who receive at least 1 administration of the investigational product and for whom any post-dose data are available will be included in the safety analysis set.

### **12.1.2 Pharmacodynamic analysis set**

All randomized patients who received at least one dose of investigational product with post-dose PD measurements available and no protocol deviation considered to significantly affect the integrity of PD results (eg, non-compliance with study drug) will be included in the PD analysis set.

### **12.1.3 Pharmacokinetic analysis set**

All randomized patients who received at least one dose of investigational product with post-dose PK measurements available and no protocol deviation considered to significantly affect PK of ticagrelor and its metabolite, AR-C124910XX, will be included in the PK analysis set.

## **12.2 Methods of statistical analyses**

### **12.2.1 General principles**

Quantitative variables will be summarized by treatment using descriptive statistics, including n, mean, standard deviation (SD), median, minimum, and maximum values.

Missing data will result in a reduced sample size for that parameter. No action will be taken to handle missing data.

A patient who withdraws prior to the last planned observation will be included in the analysis up to the time of discontinuation.

### **12.2.2 Patient characteristics**

Demographics and relevant medical and surgical history will be listed by patient and summarized by treatment group.

Categorical variables will be summarized by treatment, and time point in frequency tables (frequency and proportion). Quantitative variables will be summarized by treatment using descriptive statistics, including n, mean, standard deviation (SD), median, minimum, and maximum values.

### **12.2.3 Pharmacodynamic data**

IPA(final extent), absolute PRU and percent reduction of PRU from baseline will be listed by patient and time, and summarized by treatment group at each time point using n, arithmetic mean, SD, median, minimum and maximum TIPAmax and AUEC for final extent IPA will be summarized descriptively by treatment group and study Day 1 and 7.

Profiles of IPA (final extent), percent inhibition and percent reduction of PRU will be plotted per patient for Day 1 (0-48h post dose) and Day 7 (0-12h post dose). The corresponding arithmetic mean ( $\pm$  SD) by time point and treatment group will be plotted in one graph with treatment group indicated.

#### **12.2.4 Plasma concentrations of ticagrelor and AR-C124910XX**

All plasma concentrations will be listed by patient and time, and summarized by treatment group at each time point using n, number of samples  $\leq$  LOQ, geometric mean, CV, arithmetic mean, SD median, minimum and maximum. The CV is calculated as

$100 \cdot \sqrt{(\exp(s^2) - 1)}$ , where s is the SD of log transformed values. (Shen H et al 2006)

Individual plasma concentrations and mean by treatment group will be plotted over time by study day (Day1 and 7).

#### **12.2.5 PK parameters**

All PK parameters will be listed by patient.

All PK parameters will be summarized by treatment group and study day using n, number of samples, CV (calculated as above), arithmetic mean, SD, median, minimum and maximum.

Box plots of the PK parameters by treatment group and study day will be presented.

#### **12.2.6 Safety Analyses**

All safety data will be listed by patient and summarized by treatment group.

Adverse events will be summarized by Preferred Term and System Organ Class using Medical Dictionary for Regulatory Activities (MedDRA) vocabulary. Listings of SAEs and AEs that lead to withdrawal will be presented. The number of patients who had any AEs, SAEs, AEs that led to withdrawal, AEs with severe intensity and AEs judged as causally related to IP by the investigator will be summarized by treatment group. Where appropriate AEs will be summarized by SOC and Preferred Term by treatment group.

Serious adverse events that occur before administration of first dose will be reported separately

For continuous safety variables, the observed values and change from baseline at each time point will be summarized by treatment, and time point using descriptive statistics (n, mean, SD, minimum, median, maximum). The baseline will be defined as the last value measured prior to randomization. Shift plots of maximum value post dose versus baseline with reference limits indicated will be presented.

If a patient has more than one measurement at the same post dose occasion, then the first measurement will be used in the summaries. The extra measurement will be included in data listings. Laboratory values outside the reference limits will be listed.

For qualitative safety variables (physical examination and urinalysis) shift tables vs baseline assessment will be presented at each time point.

### **12.3 Determination of sample size**

The study data will be presented descriptively and sample size has not been determined based on statistical testing. The sample size is based on the desire to obtain adequate safety, PK, PD data to achieve the objectives of the study whilst exposing as few patients as possible to the study procedures

### **12.4 Data monitoring committee**

A data monitoring committee will not be used for this study.

### **13. IMPORTANT MEDICAL PROCEDURES TO BE FOLLOWED BY THE INVESTIGATOR**

The principal investigator(s) is responsible for ensuring that procedures and expertise are available to handle medical emergencies during the study. **A medical emergency usually constitutes an SAE and should be reported as such.** In the case of a vascular event, the patients should be discontinued from the study if administration of a prohibited concomitant medication treatment with PCI or CABG or other major surgery is needed.

The AstraZeneca representative will work with the investigator to compile all the necessary information and ensure that the appropriate AstraZeneca Patient Safety Department receives a report by Day one for all fatal and life-threatening cases and by Day five for all other SAEs.

All Serious Adverse Events (SAE) must be reported to Clinical Patient Safety, AstraZeneca Marketing Company within one day (that is immediately but not later than the end of the next business day) by fax. Clinical Drug Safety will forward the SAE report to the applicable AstraZeneca R&D. The monitor should also be informed when an SAE has occurred.

Follow-up information on SAEs must also be reported by the investigator within the same time frames.

The investigator and/or Sponsor are responsible for informing the Ethics Committee and/or the Regulatory Authority of the SAE as per local requirements.

For Serious Adverse event reporting, complete the SAE report and fax the report to the appropriate Patient Safety department.

There is no known antidote to reverse the effects of ticagrelor. The average half-life of ticagrelor is approximately 12 hours, so blood levels of ticagrelor should be low by 48 to 72 hours (ie, 4 to 6 half-lives) after discontinuation. Platelet transfusions may be given. It is not known if new platelets may be inhibited by ticagrelor as long as it is circulating in blood.

#### **13.1 Medical emergencies and AstraZeneca contacts**

The Principal Investigator is responsible for ensuring that procedures and expertise are available to handle medical emergencies during the study. **A medical emergency usually constitutes an SAE and is to be reported as such, see Section 6.3.4**

In the case of a medical emergency the investigator may contact the Study Delivery Team Leader. If the Study Delivery Team Leader is not available, contact the Study Delivery Team Physician at the AstraZeneca Research and Development.

## 13.2 Overdose

There is no known antidote to ticagrelor. In the event of overdose, adverse events should be monitored and ECG monitoring may be required. The expected effect of overdose is prolonged duration of bleeding risk. If bleeding occurs appropriate supportive measures should be taken. An overdose with associated AEs is recorded as the AE diagnosis/symptoms on the relevant AE modules in the CRF and on the Overdose CRF module.

- An overdose without associated symptoms is only reported on the Overdose CRF module.
- If an overdose on an AstraZeneca study drug occurs in the course of the study, then investigators or other site personnel inform appropriate AstraZeneca representatives immediately, or **no later than 24 hours** of when he or she becomes aware of it.

The designated AstraZeneca representative works with the investigator to ensure that all relevant information is provided to the AstraZeneca Patient Safety data entry site.

For overdoses associated with SAE, standard reporting timelines apply, see Section 6.3.4. For other overdoses, reporting should be done within 30 days.

## 13.3 Pregnancy

All outcomes of pregnancy should be reported to AstraZeneca.

### 13.3.1 Maternal exposure

If a subject becomes pregnant during the course of the study investigational product should be discontinued immediately.

Pregnancy itself is not regarded as an adverse event unless there is a suspicion that the investigational product under study may have interfered with the effectiveness of a contraceptive medication. Congenital abnormalities/birth defects and spontaneous miscarriages should be reported and handled as SAEs. Elective abortions without

complications should not be handled as AEs. The outcome of all pregnancies (spontaneous miscarriage, elective termination, ectopic pregnancy, normal birth or congenital abnormality) should be followed up and documented even if the patient was discontinued from the study.

If any pregnancy occurs in the course of the study, then investigators or other site personnel inform appropriate AstraZeneca representatives immediately, or **no later than 24 hours** of when he or she becomes aware of it.

The designated AstraZeneca representative works with the investigator to ensure that all relevant information is provided to the AstraZeneca Patient Safety data entry site within 1 or 5 days for SAEs, see Section 6.3.4 and within 30 days for all other pregnancies.

The same timelines apply when outcome information is available.

The PREGREP module in the CRF is used to report the pregnancy and the PREGOUT is used to report the outcome of the pregnancy.

